5.4 Interim analysis

Per-patient data listings and summary tables/plots will be provided for the several DSMB meetings and as specified in the DSMB Charter.

There will be an analysis of the primary, secondary, and exploratory endpoints relating to the Parent phase once Visit 6 has been completed, and an interim CSR will be written.

Intra BIO

Clinical Study Reference: IB1001-202

5.5 Baseline characteristics

5.5.1 Inclusion/exclusion criteria

An individual patient listing of the deviations from inclusion and exclusion criteria will be presented.

5.5.2 Demographics

Demographic data at baseline will be summarized for all patients and by the 4 age/weight/dosing groups in tabulations.

Appropriate descriptive statistics for age, height, weight, BMI, ethnic group and sex will be given. The summary will be created for each analysis population separately. Additionally, demographic data will be listed.

5.5.3 Baseline characteristics

The following relevant patient baseline characteristics will be listed and summarized overall (frequency and percentage) and are considered key subgroups. The subgroups differentiated on a median value will use the median value as determined for the specific analysis population.

- Naïve versus non-naïve as determined at screening
- Age (paediatric versus adult)
- Gender (male versus female)
- Age/weight/dosing group
- Region (US versus EU)
- Selected Primary Anchor Test (9HPT-D or 8MWT)
- Tay-Sachs versus Sandhoff Patients
- SARA Subtest Gait: classification based on below (\leq)/above the median value at Visit 1.
- Composite of SARA Subtests 1- 4 (Gait, Stance, Sitting, Speech): classification based on below (≤)/above the median value at Visit 1.
- Intra-Patient variability between SARA score at Visit 1 (Baseline 1) vs Visit 2 (Baseline 2): classification based on below (≤)/above the median value of the difference between the two visits.
- Intra-Patient variability between CI-S score (for primary anchor only) Visit 1 (Baseline 1) vs Visit 2 (Baseline 2): classification based on below (≤)/above the median value of the difference between the two visits.
- Age of diagnosis: Infantile (<2 years), Juvenile (2 to <15 years), Adolescent/Late Onset (≥ 15 years)
- Disease severity: classification based on below (≤)/ above the median SARA score at Visit 1.

5.5.4 Disposition

A summary table will be created, stating the number of patients per site, including site number, location/country, and investigator.

To present disposition, a summary of all included, randomised, treated and completed patients will be created. Number/percentage screened will be included as well (if available in the database). Additionally, in the same summary, the number/percentage of patients in the SAF, mITT and PPS will be presented. Furthermore, the frequency and percentage per reason for non-completion will be added.

Additionally, a listing displaying all disposition information (including reasons for withdrawal and reasons for exclusion from the analysis population, if available electronically) on a per patient level will be created. This listing will include follow-up time for each patient, calculated from date of first dose until end of study for the Parent phase.

5.5.5 Medical history

Medical history will be tabulated per System Organ Class (SOC) and Preferred term (PT) according to the Medical Dictionary for Regulatory Activities (MedDRA) terminology list and presented as number/percentage of patients in each SOC and PT for the SAF. SOC and PT will be presented in descending order of frequency of occurrence based on SOC and PT. These data will also be listed on a per patient level.

GM2 Gangliosidosis specific history will be summarized as appropriate, presenting confirmed diagnosis (yes/no) and time since diagnosis. For calculation of time since diagnosis, see Section 10.1.

GM2 Gangliosidosis specific history data as collected will also be listed on a per patient level.

5.5.6 Pregnancy data

Pregnancy test result data will be listed for females of childbearing potential only, on a per visit basis.

5.5.7 Other screening data

Other data collected at screening and/or baseline only, if available, will be listed. These screening/baseline data will be presented using all subjects included in the study, if applicable.

5.6 Statistical analysis efficacy endpoints

The primary analysis population is the mITT for the primary and all secondary endpoints. Analyses of these endpoints based on the PPS will also be undertaken to provide supplementary information on efficacy. The ITT population will be used only for baseline summary tables.

Analyses of the primary endpoint based on the mITT population will utilise a last observation carried forward (LOCF) approach for missing/unreadable videos at Visit 5 and Visit 6. For the primary endpoint CI-CS, this implies that the CI-CS value for Visit 4 to Visit 6 will be assigned the value 0 (stable) if both videos at Visit 5 and Visit 6 are unavailable.

Also for the key secondary endpoint, Change in Severity Score based on Averaged Clinical Impression of Severity (CI-S), it is assumed that if both videos are missing/unreadable for the baseline (Videos from Visit 1 or 2), treatment (Videos from Visit 3 or 4), or washout (Videos from Visit 5 or 6) period, the change from one period to another will be assigned the value 0 (stable).

Clinical Study Reference: IB1001-202

A sensitivity analysis for missing data will be performed for the statistical analyses to compare patient's outcome on the primary outcome measure and their compliance throughout the study. The robustness of the primary analyses in the mITT analysis set will be assessed as follows:

• If either video for Visit 3 or Visit 4 is available but both videos for Visit 5 and Visit 6 are not available, then the value -1 (worsening) will be used instead of 0 for the CI-CS for Visit 4 to Visit 6 unless the missingness is due to a technical reason (MCAR, e.g. due to machine failure).

For each of the primary and secondary endpoints there will be separate descriptive statistical displays within the key subgroups as listed in Section 5.5.3 without any statistical analysis. For the subgroup presentations, only the mITT population will be used. Spaghetti plots will not be created for the subgroup analyses; these will be presented in forest plots (one for each endpoint, excluding the SARA -, SAFI - and mDRS subscores and excluding the EQ-5D-5L/Y), presenting the mean or (pseudo-)median with a 90% two-sided CI, using a stem at mean or median difference of 0, where applicable. Upon discretion of the programmer, the forest plots may be presented as two plots: one for Visit 4 versus Visit 2 and one for Visit 6 versus Visit 4.

Considering the number of subgroups, the forest plots may become unclear and indecipherable. When that occurs, a split will be made into two forest plots for the endpoints: one for the first 7 subgroups, and one for the remaining.

All individual primary and secondary endpoint data will be listed as well.

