3.1.3 Target Number of Patients

- To be enrolled: Approximately 39 patients
- To be analyzed according to the modified Intention to Treat (mITT) analysis: Approximately 36 patients
- To be analyzed according to the Per Protocol Analysis: Approximately 30 patients

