3 SUBJECTS FOR ANALYSIS

3.1 Parent study: Analysis populations

3.1.1 Intention-to-Treat (ITT) population

The ITT population will consist of all patients who receive at least one dose of study drug (N-Acetyl-L-Leucine) and with one video recording at either Visit 1 or Visit 2 (or both).

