3.1.2 Modified Intention-to-Treat (mITT) population

The mITT population will consist of all patients who receive at least one dose of study drug (N-Acetyl-L-Leucine) and with one video recording at either Visit 1 or Visit 2 (or both) and one video recording at either Visit 3 or Visit 4 (or both).

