3.1.3 Per Protocol Set (PPS)

The PPS will consist of all patients with at least one video recording at baseline (either Visit 1 or Visit 2), end of treatment (either Visit 3 or Visit 4), and end of washout (either Visit 5 or Visit 6) and without any major protocol deviations that can influence the validity of the data for the primary efficacy variable.

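### A dosed patient with no Visit 3 or Visit 4 video enters no efficacy analysis, and no planned sensitivity run gives such a patient an unfavourable score

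*SAP*

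**What the plan says.** SAP 3.1.1 starts the ITT definition with exposure ("The ITT population will consist of all patients who receive at least one dose of study drug") and adds a video at Visit 1 or Visit 2. SAP 3.1.2 builds mITT from the same two conditions plus a third that can be met only after treatment has begun: "one video recording at either Visit 3 or Visit 4 (or both)". The per-protocol set (SAP 3.1.3) also needs a Visit 3 or 4 video, and a washout video as well.

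SAP 5.6 then assigns the sets: "The primary analysis population is the mITT for the primary and all secondary endpoints". The per-protocol set is the supplement: "Analyses of these endpoints based on the PPS will also be undertaken to provide supplementary information on efficacy". For the remaining set: "The ITT population will be used only for baseline summary tables". The table list in SAP 11.3 agrees, since ITT appears only under demographics and baseline characteristics. Protocol 8.5 also names mITT as the primary efficacy set, so the two documents are consistent.

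The missing-data sensitivity analysis in SAP 5.6 is triggered as follows: "If either video for Visit 3 or Visit 4 is available but both videos for Visit 5 and Visit 6 are not available". It then uses -1 instead of 0 for the Visit 4 to Visit 6 score, unless the video is missing for a technical reason. SAP 7 limits it to the primary analysis of the parent study.

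**The concern.** Entry to the primary set depends on something observed after the first dose. In a single-arm trial tested against zero, there is no control group in which similar losses would offset it. If patients leave before Visit 3 because they worsen or cannot tolerate the drug, the mean among those who remain is higher than the mean among those treated.

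Nothing else in the visible plan closes the gap:

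- The early termination visit records the anchor-test videos (Protocol 7.1.7), but no rule lets such a video count towards mITT or the primary endpoint.
- SAP 5.3 keeps withdrawn patients' data up to their last assessment, but these patients have already failed the mITT condition.
- SAP 5.6 gives a CI-S change of 0 when both videos of a period are missing or unreadable. Within mITT a treatment-period video already exists, so for that period the rule can matter only for unreadable videos.
- The extension set starts from patients who completed Visit 6.
- The disposition table in SAP 5.5.4 lists the safety, mITT and per-protocol counts but not ITT, although Protocol 8.1.1 asks for ITT. The size of the gap would not be visible there.

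At stake is whether a reader of a modestly positive result could tell if it depends on who was left out.

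**Working it through.** **The plan's own figure.** The planning distribution (Protocol 8.10, SAP 2.4.1) puts 30% of patients evenly on 1 and 2, and 70% evenly on -1, 0 and 1. The probabilities are 0.2333 for -1, 0.2333 for 0, 0.2333 + 0.15 = 0.3833 for 1, and 0.15 for 2.

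- Mean = -0.2333 + 0.3833 + 2(0.15) = 0.45.
- Variance = (0.2333 + 0.3833 + 4(0.15)) - 0.45² = 1.2167 - 0.2025 = 1.0142, so SD = 1.007. With the n-1 correction at n=30 this is 1.024; the plan states 1.02.
- Power at n=30, one-sided 5%, from the noncentral t with 29 df and noncentrality 0.45/1.02 × √30 = 2.416, is 76.3%. The stated 76% reproduces.

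**Direction of the existing sensitivity run.** The endpoint is (Visit 2 to 4 score) minus (Visit 4 to 6 score). Replacing 0 by -1 in the second term changes the endpoint by -(-1) - 0 = +1 for each patient affected. The run can raise the mean or leave it alone; it cannot lower it.

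**Number affected.** Protocol 3.1.3 plans about 39 enrolled, and for mITT: "To be analyzed according to the modified Intention to Treat (mITT) analysis: Approximately 36 patients". The difference is 39 - 36 = 3, or 7.7%. This is a ceiling, because the gap may include patients never dosed or without a baseline video. I take k = 0 to 3 as an assumption.

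**Effect on the test.** Take n=36 mITT patients with observed mean m and SD s = 1.007, and add k patients with endpoint value c. Here c = -1 means a Visit 2 to 4 score of -1 and a Visit 4 to 6 score of 0. Then:

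- new mean M = (36m + kc)/(36 + k)
- new variance V = [35s² + 36m² + kc² - (36 + k)M²]/(35 + k)
- t = M/√(V/(36 + k)), with 35 + k df

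Worked case, m = 0.30, k = 3, c = -1: M = (10.8 - 3)/39 = 0.20. The sum of squares is 35(1.007²) + 36(0.09) + 3 = 41.73. V = (41.73 - 39 × 0.04)/38 = 1.057. t = 0.20/√(1.057/39) = 1.215 on 38 df, so p = 0.116.

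| Observed mITT mean | none added | 1 at -1 | 2 at -1 | 3 at -1 | 3 at 0 |
|---|---|---|---|---|---|
| 0.30 | 0.041 | 0.061 | 0.086 | 0.116 | 0.041 |
| 0.45 | 0.006 | 0.010 | 0.016 | 0.025 | 0.006 |

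At m = 0.40, three patients at -1 give p = 0.043. At the planned mean of 0.45, the same three lower the estimate to (16.2 - 3)/39 = 0.338.

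**The case against.** The choice of set is deliberate and consistent across both documents. This is a Phase II study in which the 5% level is only a guide (Protocol 8.2). The patients concerned are not hidden: they stay in the safety set, in disposition with reasons for non-completion, and in the listings. All of that stands, and it is why the primary set need not change.

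Three stronger readings are tempting, and the documents do not support them.

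- A reader might infer that everyone who stops early for intolerance or worsening is dropped. That is not so. Protocol 4.3 asks patients who discontinue drug to complete the remaining visits, and one video at Visit 3 or Visit 4 keeps them in mITT.
- A reader might infer that the plan expects three such losses. It gives only enrolled and mITT targets. It states neither the number dosed nor the ITT size, and patients can be withdrawn before dosing, for example after a positive Visit 1 urine test.
- A reader might infer that the mITT mean is biased upward. mITT selects on whether a video exists, not on its score. Under the COVID-19 provisions, in-person Visit 3 may be skipped and remote visits are not video-recorded, although Visit 4 may only be postponed. Absence for such reasons need not relate to outcome.

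It is also fair to say that the size rests on assumed inputs: scoring the patients 0 leaves the p-value where it was. What survives is that no run in the visible documents tests a value below 0 for these patients.

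**Conclusion.** The gap is real but narrow. It concerns only dosed patients with a baseline video and no video at Visit 3 or 4, and the visible documents give them no place in any efficacy estimate or test. Upward bias is possible if they left because of worsening or intolerance; it is not shown. The only missing-data sensitivity analysis moves the endpoint in the drug's favour, so the unfavourable direction is untested.

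On the assumptions of 36 mITT patients, SD 1.007 and up to three affected patients scored -1, a result near 0.30 would lose nominal significance with a single such patient. A result at 0.40 or 0.45 would keep it with all three. Only near-borderline results are sensitive. COVID-19 Addendum 1, which may contain further analysis rules, could not be checked.

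**What to change.** Keep mITT as the primary set. In SAP 5.6, add one prespecified sensitivity analysis of the primary endpoint on the existing ITT set, using the same test:

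- When neither Visit 3 nor Visit 4 has a usable video, set the Visit 2 to 4 score to -1 and the Visit 4 to 6 score to 0.
- When the absence is for a technical reason, set the Visit 2 to 4 score to 0 instead. This matches the exemption in the existing rule and should be classified in the same way, before database lock.
- State whether an early termination video exists for each such patient and that it is not used in this run, so that the omission is explicit.

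In SAP 5.5.4, add the ITT count and the number in ITT but not mITT, with reasons.

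The cost is one extra run and a line or two in the disposition table, with no new data, visits or patients. The downside is a supporting figure that may be less favourable. If no patient falls in the gap, the run gives the same result as the primary analysis.

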8.5.1 Primary Efficacy Endpoint

The primary endpoint for the study is based on blinded raters' Clinical Impression of Change in Severity (CI-CS) comparing videos showing the patient's change in performance over 42 days (+7 days) on a pre-defined anchor clinical symptom scale: either the 9 Hole Peg Test of the Dominant Hand (9HPT-D) or the 8 Meter Walk Test (8MWT). A manual will be provided to each clinical site, which provides instructions for the administration of the CI-CS [Fields, 2020]. Similarly, a video-acquisition manual will be provided, which provides instructions for making standardized videos of the 8MWT and 9HPT-D primary anchor tests The comparison of the Visit 4 video with the Visit 2 video and the comparison of the Visit 6 video with the Visit 4 video will provide the scores that contribute to the primary endpoint. Each of these comparisons will score change on a 7-point Likert scale (+3=significantly improved to -3= significantly worse).

During the pre-treatment period, the treating physician will evaluate each patient's clinical symptoms and select, at **Visit 1**, either the 9HPT-D or 8MWT as the primary anchor around which the CI-CS assessment will be scored. A cognitive assessment should be performed at **Visit 1** according to standard procedures of the clinical site to assist with the selection of the anchoring functional test appropriate for each patient from both a cognitive and a motor perspective.

The primary evaluation of the CI-CS will be performed by two independent raters whose assessments will be based on videos of the anchor test taken at each visit. These raters will be blinded to the treatment periods (baseline, treatment, or washout) to reduce detection and performance bias.

The primary endpoint is defined as the CI-CS comparing end of treatment with N-Acetyl-L-Leucine (Visit 4) with baseline (Visit 2) minus the CI-CS comparing the end of washout (Visit 6) with the end of treatment with N-Acetyl-L-Leucine (Visit 4) based on the primary anchor test.

The CI-CS assessment will instruct the blinded rater to consider: 'compared to the first video, how has the severity of their performance on the 9HPT-D or 8MWT changed (improved or worsened) in 6-weeks as observed in the second video?'

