8.6 Missing Data

The primary endpoint will utilize assessments based on single video recordings at the end baseline period (Visit 2), end of the treatment period (Visit 4), and end of the washout period (Visit 6). If the Visit 2 video is missing, the Visit 1 video will be used in its place. Similarly, if the Visit 4 and Visit 6 videos are missing, Visit 3 and Visit 5 videos will respectively be used in their place.

Analyses based on the mITT analysis set will utilize a last observation carried forward (LOCF) approach for missing videos at Visit 5 and Visit 6. For the primary endpoint CI-CS, this implies

¹⁶The 9 Hole Peg Test of the Dominant Hand (9HPT-D) and the 8 Meter Walk Test (8MWT), will be videoed for every patient at every visit except Visit 0

¹⁷ European Sites Only

that the CI-CS value for **Visit 4** to **Visit 6** will be assigned the value 0 (stable) if both videos at Visit 5 and Visit 6 are unavailable.

A sensitivity analysis will be undertaken to assess the robustness of the primary analysis of the primary endpoint in the mITT analysis set as follows:

If either video for Visit 3 or Visit 4 is available, but either video from Visit 5 and Visit 6 are unavailable, impute the value -1 (worsening) instead of 0 for the CI-CS for Visit 4 to Visit 6, unless the missingness is due to a "technical reason" (e.g. due to machine failure).

Additional methods to deal with missing data will be detailed in the SAP. Any changes from the SAP will be described and justified in the Clinical Study Report.

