7 CHANGES TO PROTOCOL AND OTHER RELEVANT REMARKS

Instead of Bland-Altman analyses of outcome scores at Visit 1 vs Visit 2, Visit 3 vs Visit 4, and Visit 5 vs Visit 6 as described in the protocol for the Parent study, an ICC method for agreement

Clinical Study Reference: IB1001-202

between the visits will be used instead to assess the stability of the outcome, as described in section 5.6.4. This is because no per-rater information is available in the dataset to be received, only an averaged or agreed value.

Regarding CI-S, the protocol is stating that for each assessment, the videos will be labeled as Video A, B, C, D, E, F. This is however not present in the DTA and test data from and is therefore removed from the SAP.

For Quality-of-Life measures, since the scoring is done for children with the EQ-5D-Y and for adults with the EQ-5D-5L, tabulations and analyses will be done separately for the corresponding age groups. The presentations on the VAS will be combined for children and adults.

For the Parent phase, sparse PK sampling will be collected for biochemical analysis to characterize the pharmacokinetics of N-Acetyl-L-Leucine in patients with GM2 Gangliosidosis. For the Extension phase, full PK profiles will be collected at Visit 7 and Visit 9. Creation of descriptive displays and reporting of these data is outside the scope of this statistical analysis plan. PK concentration data and PK parameters (following a population PK analysis) will be included in SDTM domains, after receipt. For the Parent phase a listing of PK concentration data will be created for inclusion in the Parent phase CSR, since the full PK report will only be available after the end of the Extension phase. Furthermore, urine tests for N-Acetyl-D-Leucine are handled by the same lab but will be included in the clinical database and will therefore be part of the CDISC datasets.

Regarding the sensitivity analysis (imputation of value -1) for missing data in the primary and secondary analyses: this is only applied to the primary analysis of the Parent phase. Regarding the LOCF/assumption of value 0 for missing data: this is only applied to the primary and one key secondary endpoint as specified in the relevant sections in this SAP.

The investigation of the intra-rater correlation cannot be performed, since the **sector** data do not differentiate the data per rater but rather provide an average or agreed value. Therefore, this analysis has been removed from the SAP.

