Considering the primary endpoint of the Extension phase is a different one then the primary endpoint of the Parent Study, the trial is called successful only when the primary endpoint of the Parent Study is positive. All analyses of the Extension phase on data collected until Visit 10 are considered secondary to ones of the Parent Study. All presentations in the Extension phase on data collected after Visit 10 are exploratory and descriptive.

The analysis on ASIS as described in the protocol has been removed from the SAP, as there are too limited datapoints available to perform the analysis.

For some patients, repeat visits were scheduled if measurements could not be fully handled during the agreed visit. Repeat visits will be listed for BDRM, and during BDRM or Clean File meeting it will be decided how the repeat data will be handled for analysis. Decisions will be documented prior to Database lock.

The addition of a short section of Covid-19 details (with reference to an addendum) has been added to the SAP and is not mentioned in the protocol.

Clinical Study Reference: IB1001-202

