Age is not collected during the Extension phase, and therefore whenever age is necessary for any calculations or presentations at Extension phase visits, it should be calculated using the respective visit date combined with the date of birth as collected at Visit 1. The same imputation rule as stated above (for calculation of age at diagnosis) will be applied.

Blinded data

The blinded results on the video-recordings (blinded rater's CI-CS and CI-S) will be received from according to the agreed transfer specifications. Recoding needs to be done using the visit schedule provided with the blinded results, since the visit review order is randomly assigned. The LOCF for video comparison is already available in the data.

SCAFI

For 8MWT, assistance of another person or using the wall as support is not allowed. However, timed 8MWT trials for participants who used "unallowable support" (another person or the wall) are entered in the database, considering these measurements are also necessary due to their relation to the primary and a number of secondary endpoints of the study based on videos of the test. Therefore, for the SCAFI analysis, the data for these patients that used either the wall or person support during the 8MWT should be made missing.

Furthermore, patients for 9HPT, the following clinical rules apply:

- if proband cannot complete trial in 5 minutes (i.e. 300 seconds) with dominant hand, move on to the trials with non-dominant hand
- if proband cannot complete one trial in 5 minutes (i.e. 300 seconds) with non-dominant hand, discontinue 9HPT

As a consequence, if in the database values >300 are entered for Trial 1 and/or 2, the approach for handling these data in regards to SCAFI will be:

Clinical Study Reference: IB1001-202

- In the case Trial 1 has a value <300 and Trial 2 has a value of >300 seconds, only the trial 1 with value <300 will be used for further analysis.
- In the case Trial 1 has a value of >300 seconds and Trial 2 has a value of <300 seconds, the data will count as missing and unable to perform due to physical limitations (as per the discontinuation rules defined above, Trial 2 should not have been conducted)
- In other instances, where only one trial is performed with a value >300 seconds, or two trials are performed with both values >300 seconds, the data will be considered missing due to physical limitations and replaced with a missing value for further analysis.

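### The one planned sensitivity run for missing washout scores can only raise the primary estimate, so it does not test robustness

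*SAP*

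**What the plan says.** Protocol section 8.5.1 defines the primary endpoint as the CI-CS comparing end of treatment "with baseline (Visit 2) minus the CI-CS comparing the end of washout (Visit 6) with the end of treatment". The scale runs from -3 (significantly worse) to +3 (significantly improved), so a larger difference favours the drug.

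For the mITT, SAP section 5.6 and protocol section 8.6 give the Visit 4 to Visit 6 score the value 0 when neither the Visit 5 nor the Visit 6 video is available. SAP section 5.6 then describes a sensitivity analysis meant to assess the robustness of the primary analysis: for those patients "then the value -1 (worsening) will be used instead of 0 for the CI-CS for Visit 4 to Visit 6", unless the video was lost for a technical reason.

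The protocol's version has a different trigger: "but either video from Visit 5 and Visit 6 are unavailable, impute the value -1 (worsening) instead of 0". The SAP requires both videos to be missing.

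SAP section 7 says of the -1 imputation that "this is only applied to the primary analysis of the Parent phase". The table list in SAP section 11.3 has one sensitivity analysis of the primary endpoint, in Table 14.2.1, for the mITT only. The PPS analysis is described as supplementary.

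**The concern.** The value -1 sounds pessimistic because it records a worse course for the patient. In this endpoint, worsening off drug counts as evidence of benefit, so -1 is optimistic about the drug.

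The primary rule covers missing patients who stayed stable. The sensitivity run covers those who lost benefit. No planned analysis covers those who improved during washout, for instance through practice or natural fluctuation. Protocol section 3.1.2 itself notes that symptoms commonly fluctuate over a week.

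A reader who sees the two runs agree could conclude that missing washout data do not matter. The agreement would carry almost no information, because the second run is nearly certain to be at least as favourable as the first.

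**Working it through.** **Inputs.** Planned mITT of about 36 and PPS of about 30; assumed mean 0.45 and SD 1.02; one-sided 5% one-sample t-test; 76% power with 30 patients (SAP section 2.4.1). The number imputed, k, is not given. The gap 36 - 30 = 6 is an upper guide only, since it also contains patients excluded for major deviations.

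**The plan's own figure.** The stated distribution puts 0.15 on each of 1 and 2 for responders, and 0.7/3 on each of -1, 0 and 1 for the rest.
- Mean = 0.15(1) + 0.15(2) + 0 = 0.45.
- Variance = 0.15(1) + 0.15(4) + (0.7/3)(2) - 0.45² = 1.2167 - 0.2025 = 1.0142, so SD = 1.007.
- Power at n = 30 is 76.3% with SD 1.02 and 77.2% with SD 1.007. The stated 76% reproduces.

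**Direction of the imputation.** Let A be the Visit 2 to 4 score, B the Visit 4 to 6 score, and D = A - B. With B = 0, D = A. With B = -1, D = A + 1. With B = +1, D = A - 1. Every imputed patient therefore moves up by exactly 1 under the planned run, and the mean moves by k/36:

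| k | shift under -1 | share of 0.45 | shift under +1 |
|---|---|---|---|
| 1 | +0.028 | 6% | -0.028 |
| 3 | +0.083 | 19% | -0.083 |
| 6 | +0.167 | 37% | -0.167 |

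If the Wilcoxon fallback is used, the Hodges-Lehmann estimate cannot fall either, because no observation decreases.

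**Effect on the test.** Simulation used n = 36 and 100,000 trials per scenario. The score distributions in the two no-effect scenarios are assumptions. In the narrow one, A and B each take -1, 0, 1 with probabilities 0.2, 0.6, 0.2. In the wide one, each takes -3 to +3 with probabilities 0.02, 0.06, 0.17, 0.50, 0.17, 0.06, 0.02. Percentage of trials significant:

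| k | narrow: 0 / -1 / +1 | wide: 0 / -1 / +1 |
|---|---|---|
| 1 | 5.0 / 6.8 / 3.0 | 5.1 / 6.3 / 4.0 |
| 3 | 5.0 / 12.4 / 1.0 | 5.1 / 9.2 / 2.2 |
| 6 | 4.9 / 25.9 / 0.1 | 5.1 / 15.6 / 0.8 |

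Under the planning distribution, with imputed patients assumed to follow it when B = 0, 83.4% of trials are significant with value 0:

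| k | significant under -1 | significant under +1 | significant results lost under -1 | lost under +1 |
|---|---|---|---|---|
| 1 | 86.7% | 78.3% | 0 | 6.1% |
| 3 | 92.0% | 66.0% | 0 | 20.9% |
| 6 | 96.8% | 45.3% | 0 | 45.8% |

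**A limit on the claim.** The statement is exact for the estimate but not for the p-value, because raising an already extreme value also raises the SD. Take 36 patients: one imputed at 3, three at 1 and 32 at 0.
- Value 0: mean 6/36 = 0.167, SD 0.561, p = 0.042.
- Value -1: mean 7/36 = 0.194, SD 0.710, p = 0.055.
- Value +1: mean 5/36 = 0.139, SD 0.424, p = 0.029.

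Such datasets are rare: none of about 83,400 significant trials lost significance under -1 at any k.

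**The case against.** The strongest reply is that little depends on this run. SAP section 7 states that "the trial is called successful only when the primary endpoint of the Parent Study is positive", and the primary analysis uses 0, which this rule does not bias in the drug's favour. The number affected may be 0: a Visit 5 video replaces a missing Visit 6 video (protocol section 8.6), Visit 6 may be postponed but not skipped (protocol section 3.1.2.5.2), and technical losses are exempt. All of this stands. It means the null rejection rates above are not error rates for the trial, and k = 6 is a ceiling rather than an expectation. The rates under +1 also depend on what is assumed about the imputed patients: at k = 6, if those patients are given no treatment-period effect, about 26% of trials are significant instead of 45.3%.

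Other planned analyses offer partial cover. The PPS requires a Visit 5 or Visit 6 video, so no imputed washout score enters it. But it also admits only patients "without any major protocol deviations that can influence the validity of the data for the primary efficacy variable", and it makes no unfavourable assumption about anyone. The Visit 2 to Visit 4 component is reported separately, and SARA and SCAFI changes are tested without this imputation. Those are useful context but do not test the primary endpoint against adverse washout scores.

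Read literally, the protocol's trigger could replace an observed washout score below -1 with -1, which would lower the endpoint. Its reference to replacing 0 makes the SAP's meaning far more likely. COVID-19 Addendum 1, where further missing-data rules may sit, was not available.

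**Conclusion.** The concern holds. In the protocol and SAP text available, the only sensitivity imputation planned for the primary endpoint moves every affected patient in the drug's favour. It leaves the estimate unchanged if k = 0 and otherwise raises it by k/36, up to 0.167 at the guide maximum of 6. It cannot do the job the SAP assigns to it.

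The mean shift is arithmetic and needs only the SAP's trigger and the planned mITT size. The significance rates rest on the assumed score distributions and on k. The consequence is an uninformative supporting analysis, not an inflated trial error rate. It should be fixed, but it does not threaten the primary test.

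**What to change.** In SAP section 5.6 and protocol section 8.6, keep the -1 run if wanted and add one for the same patients with a Visit 4 to Visit 6 score of +1. Alternatively, vary one common imputed score upward from -1 and report where the one-sided p-value crosses 0.05. Give the mean and 90% confidence interval with each p-value, because p is not always monotone in the imputed score. Show the PPS result alongside as the version without imputed washout scores, noting that it also drops major deviators. Change the protocol trigger to match the SAP, so that both the Visit 5 and Visit 6 videos must be unavailable.

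The cost is a sentence or so in each document and a few program runs. Imputed zeros must be flagged so that they can be told apart from observed zeros, since SAP section 10.1 says "The LOCF for video comparison is already available in the data". The added result may look less favourable than the -1 run.
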